1. STUDY INFORMATION

Title	Comparative effectiveness of heterologous and homologous
	primary- and booster SARS-CoV-2 vaccination schedules in
	the Nordic countries
Protocol version	1.1
identifier	
Date of latest version of	22 April 2022
protocol	
EU PAS Register number	EUPAS46537
Medicinal products	Comirnaty (BNT162b2)
	Vaxzevria (ChAdOx1-S [/AZD1222])
	Spikevax (mRNA-1273 [/Moderna covid-19 vaccine])
Marketing authorization	Pfizer/BioNTech
holder(s)	AstraZeneca
	Moderna
Research question and	The overall aim of this project is to provide combined and
objectives	country-specific (Denmark, Norway, Finland, Sweden)
	estimates of SARS-CoV-2 vaccination schedule effectiveness
	using comparative study designs.
Country(-ies) of study	Denmark, Norway, Finland, and Sweden
Authors	[name]; [name]

4. ABSTRACT

Rationale and background: Both heterologous and booster vaccination schedules with covid-19 vaccines are considered instrumental in controlling covid-19. However, data to help inform on the effectiveness of these vaccination regimens in real world settings are limited.

Research question and objectives: The overall aim of this project is to provide combined and country-specific (Denmark, Finland, Norway and Sweden) estimates of covid-19 vaccination schedule effectiveness using comparative study designs.

Primary objectives:

- To provide comparative vaccination effectiveness (VE) estimates for heterologous primary (2-dose) schedules compared to homologous primary (2-dose) schedules as well as heterologous booster (3-dose) schedules compared to homologous booster (3dose) schedules.
- To provide comparative VE estimates for both heterologous and homologous booster (3-dose) schedules compared to heterologous and homologous primary (2-dose) schedules.

Secondary objectives:

- To provide comparative VE estimates for selected schedules in the periods of Alpha, Delta and Omicron dominance (with variant specific endpoint information to the extent this is possible).
- To explore a) waning of immunity comparing time-since vaccination periods within selected schedules and b) comparative waning comparing time-since vaccination across selected schedules.

Tertiary objectives:

5. To provide VE estimates comparing vaccinated to unvaccinated in a child-adolescent population of individuals aged 5 to 17 years.

Study design: Nationwide register-based cohort studies in Denmark, Finland, Norway and Sweden during the study period 27 December 2020 to 28 February 2022.

Population: Source cohorts will consist of all individuals five years of age and older at date of first vaccination. Eligibility criteria for study inclusion will be having received at least the primary immunization (ie, first and second vaccine dose against covid-19) with either AZD1222, BNT162b2, or the mRNA-1273 vaccine and no positive polymerase chain reaction

(PCR) test for SARS-CoV-2 before completing the respective 2- or 3-dose schedule under study (for the purpose of objective #5, being vaccinated will not be an eligibility criterion).

Variables: The outcomes of interest will be positive PCR test for covid-19 (primary outcome), covid-19 hospitalization (any and at an intensive care unit [ICU]) and covid-19 mortality.

Data sources: Nationwide demography- and health registers within each participating country.

Study size: We expect the Nordic countries to contribute with 19.6 million individuals vaccinated with at least two doses - based on a combined population of 23.1 million and a vaccination uptake of 85% among individuals aged 12 years or older. We expect the uptake of 2 doses among 5- to 11-year olds to be 50% in the countries where vaccination has been recommended for this age group. The exact sample size within each comparison will depend on the prevalence of the schedules being studied.

Data analysis: We will compare schedules head-to-head and provide comparative VE estimates using survival analysis to estimate risk differences and risk ratios from adjusted survival curves. We will include adjustment for age, calendar period, sex, comorbidities and vaccination priority group.

Milestones: Study preparations were initiated 25 February 2022. Start of study and data analysis will be 1 April 2022 and the study report is expected to be finalized by 30 June 2022.

5. AMENDMENTS AND UPDATES

Date	Section	Amendment or update	Reason
22-04-	Page 13	- Exclusion criteria for	Incorporating minor
22		immunocompromised	comments from EMA
		added.	assessment of protocol
	Pages	- Description of individual	1.0.
	21-22	autoimmune conditions.	
	Pages	- More details on country-	
	32-33	specific vaccination	
		strategies.	
	Page 39	- Example of how to	
		interpret comparative	
		waning.	
	Page 40	- Adding statistical code	
		review as a QA measure.	
	Page 44	- Example table for results	
		added.	
	22-04-	22-04- Page 13 22 Pages 21-22 Pages 32-33 Page 39 Page 40	22-04- 22Page 13-Exclusion criteria for immunocompromised added.22immunocompromised added.24Pages-Description of individual autoimmune conditions.21-22autoimmune conditions.Pages-More details on country- specific vaccination strategies.23-33-Example of how to interpret comparative waning.Page 40-Adding statistical code review as a QA measure.Page 44-Example table for results

6. MILESTONES

Milestones	Planned dates
Study Plan	10 March 2022
Study Protocol (posted on EU-PAS register).	31 March 2022
Registration in the EU-PAS Register	31 March 2022
Study Report (posted on EU-PAS register).	30 June 2022
Manuscript(s) ready for submission.	25 July 2022

7. RATIONALE AND BACKGROUND

At the end of 2020, mass vaccination programs against the SARS-CoV-2 virus were launched on an unprecedented global scale. The early clinical trials of the two mRNA vaccines, BNT162b2 (BioNTech-Pfizer) and mRNA-1273 (Moderna), had demonstrated surprisingly high vaccine efficacy in preventing symptomatic infection against the original strain.(1,2) This was followed by the two adenoviral vector vaccines, AZD1222 (Oxford-AstraZeneca) and Ad26.COV2.S (Johnson & Johnson-Janssen), also demonstrating their potential in combating the SARS-CoV-2 virus.(3,4) However, how clinical efficacy translates into vaccination effectiveness in the real world setting is complex. Firstly, a number of outcomes are either not included in the clinical trials or cannot be assessed due to lack of statistical power, but are still of great public health importance. This includes effectiveness against transmission, severe covid-19 and fatal covid-19. Secondly, the trial participants do not always match the target populations of mass vaccination programs well with respect to age and covid-19 risk factors. Finally, effectiveness in the observational setting is dynamic and is influenced by a number of factors, a) pathogen-level factors such as predominant variants of concern, b) individual-level factors such as waning of immunity and c) community-level factors such as the degree of herd immunity and testing patterns.

Today, it is clear, that while real world evidence does support the effectiveness of the SARS-CoV-2 vaccines, especially against severe disease, waning of immunity and the emergence of variants of concern with the potential to evade immune responses has resulted in a situation where control of the virus through immunization is a continually moving target.(5) In the current setting, key components to a successful national vaccination strategy involves a) extending the protection of individuals at risk of severe covid-19 by booster doses, and b) reducing transmission to individuals at risk of severe covid-19 by population-level boosting of immunity. To achieve these goals in practice, the use of heterologous schedules are unavoidable due to supply- and logistical issues. Thus, there is an urgent need for observational studies evaluating the effectiveness of heterologous schedules, in particular schedules involving boosting with 3rd doses.

Effectiveness of a heterologous prime-boost schedule

Heterologous AZD1222 / mRNA vaccine prime-boost schedules appear to be just as immunogenic as homologous schedules, and some studies even suggest superior immunogenicity.(6–8) However, the evidence on the effectiveness of prime-boost schedules using heterologous SARS-CoV-2 vaccines are sparse. In Denmark, the effectiveness of a dose of AZD1222 followed by a dose of mRNA vaccine was estimated in a nationwide cohort in the 9

February to 23 June 2021 period.(9) Heterologous vaccination with the combination of AZD1222 and an mRNA vaccine was associated with 88% protection against SARS-CoV-2 infection when compared to being unvaccinated. However, notable limitations include limited duration of follow-up after the 2nd dose and the use of unvaccinated as a comparison group, which may introduce bias e.g. through differences in testing patterns. In Sweden, the effectiveness of a AZD1222 / mRNA prime-boost schedule was estimated in a nationwide cohort with follow-up ending on August 23, 2021.(10) Compared to unvaccinated individuals, the prime-boost schedule provided an effectiveness of 68% against symptomatic infection in contrast to 50% for the homologous AZD1222 schedule (p<0.001). Also in this study, the duration of follow-up after the 2. dose was limited (mean duration, 76 days), precluding further exploration of waning of immunity. In Finland, effectiveness against covid-19 hospitalization was also high, >95% for heterologous AZD / mRNA schedules (compared to unvaccinated) among healthcare professionals.(11)

Effectiveness of 3rd dose boosting schedules

It is now clear that the protection against infection afforded by the currently available SARS-CoV-2 vaccines dissipates quickly in contrast to protection against severe covid-19.(12) This fact, together with the emergence of the Omicron variant of concern has highlighted the need for further boosting of immunity in the general population. Immunogenicity and reactogenicity data from phase 2 trials supports that 3rd dose schedules are associated with 1) many fold increases in neutralization antibody levels shortly after vaccination compared to shortly after 2nd dose schedules, and 2) comparable reactogenicity to 2nd dose schedules.(13) In the COV-BOOST study, both homologous and heterologous 3rd dose schedules were evaluated for seven SARS-CoV-2 vaccines.(14) The mRNA vaccines as 3rd doses demonstrated the highest increases in neutralizing antibody levels in both homologous and heterologous schedules. Reactogenicity and safety was broadly similar, except for increased reactogenicity in schedules with mRNA-1273 as a third dose.

A number of observational studies, in particular from Israel, have now provided real-world evidence on the effectiveness of 3. dose schedules.(15–18) In a matched cohort study of a large Israeli health service database including more than 1.4 million individuals, estimated effectiveness against covid-19 hospitalization, severe covid-19 and fatal covid-19.(17) Compared with receiving only two doses at least 5 months ago, a third dose of BNT162b2 effectively protected against the study outcomes. Follow-up after the 3. dose was limited (median follow-up, 13 days) and thus the study does not provide insights into waning of immunity. In Israel, only the mRNA vaccines are approved for use, and BNT162b2 has been predominantly used. Consequently, the Israeli studies do not inform us on heterologous 3. dose schedules. In a test-negative case-control study using National Health Service data from the UK, a heterologous 3. dose schedule with 2 doses of AZD1222 followed by BNT162b2 was effective against symptomatic infection, both when compared to unvaccinated and individuals with 2 vaccinations.(19)

Effectiveness against Omicron

The emergence of the Omicron variant of concern at the end of 2021 poses a significant challenge to the current vaccination programs. Immunogenicity studies have revealed that two doses provide many fold lower levels of neutralizing antibodies against Omicron than against the original Wuhan strain, and that three doses are needed to provide neutralizing antibody levels comparable to levels observed against the Wuhan strain following two doses.(20) The majority of the real-world evidence on vaccination schedules have been generated during a period where the Alpha and Delta variants have dominated. Studies of effectiveness against Omicron are currently rare. In the UK, a two-dose schedule provided little to no protection against symptomatic infection with the Omicron variant, while a third dose of BNT162b2, both in a homologous- and a heterologous schedule, provided protection of 75.5% and 71.4%, respectively.(21) In Denmark, effectiveness against infection with Omicron was moderate (55.2%) in the first month after two doses and declined rapidly. A third dose re-established the moderate protection against infection (54.6%).(22)

8. RESEARCH QUESTION AND OBJECTIVES

The overall aim of this project is to provide combined and country-specific (Denmark, Finland, Norway and Sweden) estimates of SARS-CoV-2 vaccination schedule effectiveness using comparative study designs.

Primary objectives:

- To provide comparative vaccination effectiveness (VE) estimates for heterologous primary (2-dose) schedules compared to homologous primary (2-dose) schedules as well as heterologous booster (3-dose) schedules compared to homologous booster (3dose) schedules.
- To provide comparative VE estimates for both heterologous and homologous booster (3-dose) schedules compared to heterologous and homologous primary (2-dose) schedules.

Secondary objectives:

- 3. To provide comparative VE estimates for selected schedules in the periods of Alpha, Delta and Omicron dominance (with variant specific endpoint information to the extent this is possible).
- To explore a) waning of immunity comparing time-since vaccination periods within selected schedules and b) comparative waning comparing time-since vaccination across selected schedules.

Tertiary objectives:

5. To provide VE estimates comparing vaccinated to unvaccinated in a child-adolescent population of individuals aged 5 to 17 years.

In objective #1, our aim is to answer the question *are heterologous schedules non-inferior compared to homologous schedules*? In objective #2, our aim is to answer the question *what additional benefits will a third dose provide*?

For objectives #3-#5, we will only evaluate schedules where we have sufficient information, e.g. our evaluation of waning of immunity in 2-dose schedules will be limited to the dose interval between the 2. and 3. dose and in 3-dose schedules by the end of study period. Similarly, in variant-specific analyses, we are restricted by the close period-specific correlation between available schedules and dominating variants.

9. RESEARCH METHODS

9.1 Study setting and period

The comparative effectiveness objectives will be addressed through nationwide register-based cohort studies in Denmark, Finland, Norway and Sweden during the study period 27 December 2020 to 28 February 2022. The study period end of 28 February 2022 has been chosen to reflect the significant change in testing strategy in several Nordic countries in the beginning of March 2022.

The Nordic countries provide a unique setting for the study of SARS-CoV-2 vaccination effectiveness. Firstly, the ubiquitous nationwide demography- and health registers, which includes SARS-CoV-2 immunization and surveillance registers, allow for study cohorts with a combined size of 20 million vaccinated individuals. Secondly, both pandemic control, testing and vaccination strategies have varied significantly between countries, allowing for the exploration of heterogeneity in effectiveness accordingly. Finally, the Nordic countries already

have a proven record of accomplishment in conducting rapid vaccination effect evaluations during the pandemic.

9.2 Study design

The source cohort will consist of all individuals aged five years and older as ascertained by the date of first vaccination. The main cohort will consist of individuals aged 18 years or older. We will examine an additional cohort of individuals aged 5 to 17 years old in tertiary analyses – note that not all countries can contribute information in the 5- to 11-year olds. The cohort participants will be classified according to SARS-CoV-2 vaccinations received and followed from the 2. or 3. dose using survival analysis. For 5- to 11-year olds, only the BNT162b2 in a reduced dose has been approved for use (since 25 November 2021). We will apply different study designs according to the objective in question; see subsection *Statistical Analysis* below.

Eligibility criteria for study inclusion will be:

- having received at least the primary immunization (i.e. 1. and 2. vaccine dose against covid-19) with either AZD1222, BNT162b2 or the mRNA-1273 vaccines (for the purpose of objective #5, being vaccinated will not be an eligibility criterion),
- known residency within the specific country,
- and no positive reverse transcription polymerase chain reaction (PCR) test before the study period start and before receiving a 2. or 3. dose in the distinct schedule evaluated.

EMA has previously advised that groups of people with severely compromised immune systems should be offered a 3. dose at least 28 days after the 2. dose as part of their primary vaccine series (https://www.ema.europa.eu/en/news/comirnaty-spikevax-ema-recommendations-extra-doses-boosters). Thus, a short inter dose interval (28-days to 90-days) between the 2. and 3. dose, will be an exclusion criteria.

We will use comparative designs to evaluate the majority of the objectives; thus, we will avoid comparisons with unvaccinated individuals. This will reduce concerns about bias due to inherent differences in who chooses to remain unvaccinated during the pandemic as well as concerns about healthy vaccinee bias whereby individuals recently vaccinated may be healthier than unvaccinated individuals, since current illness can delay vaccination appointments. This will also reduce concerns about ascertainment bias due to differences in testing behavior between vaccinated and unvaccinated groups. Finally, the research questions at hand are inherently comparative in the real-world setting of a completed mass vaccination rollout. Therefore, it is not a matter of vaccine vs no vaccine, but whether a heterologous schedule is non-inferior to a homologous schedule with respect to comparative VE and whether a third

dose increases VE compared to two doses. Individuals who remain unvaccinated at this point in time, are unlikely to be swayed by further real-world evaluations of effectiveness.

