At the day an individual receives a 3. dose (i.e. the index date) of the studied schedule, the individuals will be matched with an individual having received the respective 2-dose comparison schedule (i.e. controls) but have not yet received a 3. dose (i.e. at the this date). For each matched pair, the index date of the individual in the 3-dose studied schedule will be assigned to the 2-dose comparison schedule control individual. The matched controls will be eligible to be included in a 3-dose studied schedule group in case of receiving a future 3. dose to that of the given matched date. Individuals from the 3-dose studied and the 2-dose comparison schedules will be matched on age (5-year bins), calendar month of receiving the 2. dose and a propensity score summarizing potential confounders such as sex, vaccination priority group and comorbidity. The time at which an individual was vaccinated with a 2. dose, is highly correlated with risk of severe covid-19 and/or risk behavior due to the national prioritization of the rollout of the covid-19 vaccines (e.g. individuals of high risk of severe covid-19 and health care workers were prioritized for earlier vaccination than the general public).

Individuals in the country-specific cohorts will be followed from the time they enter one of the vaccination schedules groups and 13 days have passed until one of the endpoints included in the study, end of endpoint ascertainment period, received a booster dose (a 3. dose for 2-dose schedules and a 4. dose for 3-dose schedules), exit from the cohort due to death, loss to follow-up, emigration, or end of study period, whichever occurs first. I.e. for the 3- vs. 2-dose matched comparisons, follow-up for the matched pairs will also end if the control individual receives a 3. dose (on that date; see example in Figure 4B). Follow-up will be conducted separately for each outcome without censoring for the other study outcomes. That is, when evaluating effectiveness against covid-19 hospitalization to an ICU, having a positive PCR test for SARS-CoV-2 or being covid-19 hospitalized does not right-censor the follow-up for this individual. However, note that when the 14 days and 30 days, respectively, after a positive test has passed, the follow-up will be censored in the analyses of hospitalization and ICU, and mortality, respectively.

[figure not shown]

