9.8 Supplementary analyses and quality control

Quality control will be conducted indirectly to evaluate the validity of our main analyses, by making sure that 1) the prevalences of the different schedules and the number of study endpoints match national surveillance dashboards and reports, 2) conduct comparisons between 2-dose schedules and unvaccinated for all study endpoints, to make sure that we are able to recover VE estimates compatible with the current evidence, and 3) utilize a test-negative study design for selected main comparisons.

We will ensure the scientific quality of the work, by division of review tasks (including statistical code review) and responsibilities in a timely fashion and by adhering to the ENCePP Code of Conduct (see attachment).

Quality control analysis: 2-dose vaccine schedules vs. unvaccinated

Individuals having received homologous primary (2-dose) vaccine schedules of BNT162b2 and mRNA-1273 (i.e. the two most common schedules) will be compared with unvaccinated individuals (controls) with a study design similar to that for objective 2 (i.e. the 3- vs. 2-dose comparison) and as previously done.(47) In these sensitivity analyses, we will evaluate the infection endpoint (positive PCR test for SARS-CoV-2). Vaccinated individuals will be matched 1-to-1 (same matching variables as the main design [except, this analysis will not include calendar month of receiving the 2. dose as not applicable] – age, sex, comorbidity and vaccination priority group) with individuals that were unvaccinated at the vaccinee's day of vaccination. Follow-up will start on day 14 after the 2. vaccine dose (for both the vaccinated and unvaccinated controls [i.e. unvaccinated controls will be assigned the index date of the vaccinated matched individual]) and end at: the day of testing positive, exit from the cohort due to death, loss to follow-up, emigration, vaccination of the matched unvaccinated control or

receipt of a (third) booster dose for vaccinated persons, or end of study period, whichever occurs first. Individuals that will be included as unvaccinated controls will also be eligible to enter the study as vaccinated. Survival curves for vaccinated and unvaccinated-control groups will be estimated using the Kaplan-Meier estimator yielding cumulative incidences at day 75 after start of follow-up. We will calculate 95% confidence intervals using the percentile bootstrap method with 1000 repetitions.

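### In the 3- vs 2-dose matching, the no-prior-infection rule stops at each person's own schedule dose, so people infected between dose 2 and the index date can enter only the control arm

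*Protocol*

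**What the plan says.** Section 9.2 requires no positive PCR "test before the study period start and before receiving a 2. or 3. dose in the distinct schedule evaluated". The abstract states the rule as no positive PCR test "for SARS-CoV-2 before completing the respective 2- or 3-dose schedule under study". Both tie the check to a vaccine dose.

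For objective 2, Section 9.7 draws the control as a person "having received the respective 2-dose comparison schedule (i.e. controls) but have not yet received a 3. dose". It adds that "the index date of the individual in the 3-dose studied schedule will be assigned to the 2-dose comparison schedule control individual". Pairs are "matched on age (5-year bins), calendar month of receiving the 2. dose and a propensity score", the score covering factors such as sex, priority group and comorbidity. Prior infection is not named as a matching variable or in the propensity model. Section 9.2 also states that "a short inter dose interval (28-days to 90-days) between the 2. and 3. dose, will be an exclusion criteria".

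In the quality-control comparison with unvaccinated people (Section 9.8), "unvaccinated controls will be assigned the index date of the vaccinated matched individual". Section 9.7 applies a design like that of objective 2 to children aged 5 to 11 compared with unvaccinated children.

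**The concern.** A matched design of this kind needs both members of a pair to meet the same entry conditions on the same date. Here the boosted member is screened for infection up to dose 3, which is the index date. The control is screened only up to dose 2, and time zero is then moved forward to the partner's date.

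Someone infected in between is an admissible control but is barred from the 3-dose arm if boosted later. Section 9.2 itself remarks that being ill can put off a vaccination, so such people may be over-represented among those not yet boosted.

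At stake is the infection result of a primary objective. If earlier infection protects, the control arm carries extra immunity that the boosted arm cannot have. Unvaccinated controls have no schedule dose at all, so only the clause on the start of the study period binds them.

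**Working it through.** The plan gives no figure for this point, so the check compares the rules and then illustrates the size.

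**Rules compared at the pair's index date**
- Boosted member: no positive PCR before dose 3, which is the index date.
- 2-dose control: no positive PCR before dose 2 and none before the study period start; no dose 3 yet. Nothing further.
- Length of the gap: dose intervals of 28-90 days are excluded, so the boosted member's interval is generally over 90 days. Matching on month of dose 2 puts the control's interval within about a month of that.
- Effect of the study period clause: if the start is 27 December 2020 (Section 9.1), the whole gap since dose 2 is open. If it is the booster rollout (Section 9.7, objective 2), the gap runs from rollout to the matched date. For Denmark, 6 September 2021 to 28 February 2022 gives at most 175 days, and close to zero for the first pairs.

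**Infection endpoint (illustration)**

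Assumptions not in the documents: a share s of controls has such an infection, and their later risk is lower by a fraction p. Control risk is then r0 × (1 − s·p), while the boosted arm has s = 0. With VE = 1 − RR:

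observed VE = 1 − (1 − true VE)/(1 − s·p)

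For a true VE of 50%:
- s = 5%: 1 − 0.5/0.96 = 47.9% (p = 0.8); 1 − 0.5/0.955 = 47.6% (p = 0.9).
- s = 10%: 1 − 0.5/0.92 = 45.7%; 1 − 0.5/0.91 = 45.1%.
- s = 20%: 1 − 0.5/0.84 = 40.5%; 1 − 0.5/0.82 = 39.0%.

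**Death within 30 days of a positive test**

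Follow-up opens on day 14. A control positive d days before the index date can die on day 14 or later and still be within 30 days only if d is 1 to 16. Assume constant incidence and a test-to-death lag uniform on 1-30 days. The chance that the lag falls between 14 + d and 30 is (17 − d)/30. Summing over d = 1 to 16 gives 136/30 = 4.53 day-equivalents, and 4.53/75 = 6.0% of control deaths in the 75-day window. No boosted person can contribute such a death. A true VE of 50% would read 1 − 0.5 × (75 − 4.53)/75 = 53.0%, a shift upward.

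**Hospitalization and ICU**

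The positive test must fall no more than 14 days before admission (Section 9.3). A test on day −1 can therefore support an admission on day 13 at the latest, before follow-up opens. Section 9.7 also censors these analyses once 14 days have passed after a positive test.

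**The case against.** - **Pair-level reading.** The abstract's wording could mean the schedule being studied, which in objective 2 is the 3-dose one, and its date is assigned to the control. This is strained. Both statements name a second or a third dose, and a control has no third dose on the index date. The reading works only if the partner's dose is meant, which the text does not say.
- **Study period start.** If this means booster rollout, controls infected between dose 2 and rollout are already out. This stands as a possible reading. It narrows the gap without closing it, and what remains covers Delta and Omicron time.
- **No reinfection endpoint.** Infection is recorded as yes/no by date of positive PCR, so a person already positive might be treated as not at risk. This stands in part. The main analysis gives no rule for repeat positives, whereas the test-negative check in Section 9.8 has a 90-day rule. Dropping earlier positives would close the gap for infection; counting lingering positives as new events would push VE upward.
- **Missing material.** Figures 3 and 4 are not shown, and an analysis plan may add a condition at matching. That is possible, but the point rests on the eligibility rule as stated, not on silence alone.
- **Size.** The infected share, the protection and the lag are all assumed. This stands in full.

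**Conclusion.** Followed as written, the rule lets people with a positive PCR between dose 2 (or rollout) and the index date into the control arm only. The main consequence is for the primary infection endpoint of objective 2: booster VE is likely too low if earlier infection protects and those people remain at risk of a counted event. A fall from 50% to about 45-48% illustrates the order of magnitude at a 5-10% share with 80-90% protection. The effect on 30-day death is smaller and opposite in sign, about 6% of control deaths under constant incidence and a uniform lag.

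A reader might infer more, and the documents do not support it:
- *That all booster VE estimates are biased.* Hospitalization and ICU are essentially unaffected, given the 14-day test window and the day-14 start. This takes the 14-day censoring to cover tests before the index date, which Section 9.7 does not say expressly.
- *That the bias is large.* Shares of 20% or more have no basis in the documents.
- *That its direction for infection is certain.* It depends on how repeat positives count.

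Objective 1 is not touched, since both arms are indexed on their own last dose. The comparisons with unvaccinated people share the gap but are tertiary or quality-control analyses.

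**What to change.** Amend Sections 9.2 and 9.7 and align the abstract: in every matched analysis (objective 2, the comparisons with unvaccinated children under objective 5, and the unvaccinated check in Section 9.8), both members of a pair must have no positive PCR before the pair's shared index date, checked when the control is drawn. Under the model above this sets s to zero in both arms and removes the one-sided deaths. It takes one sentence and one filter on data already linked. The cost is slightly fewer eligible controls.
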